5.3.3.2. Multiple Testing Procedure

The testing procedure for across the primary and secondary endpoints is fully described in Section 5.4.2.2. Generally, a fixed sequence approach is applied, where the primary hypothesis is first in sequence and no secondary hypothesis will be tested in a confirmatory manner if the test of the primary hypothesis was not significant.

5.3.3.3. Sensitivity Analyses

Two types of tipping point analyses and an analysis using multiple imputation of missing data under missing at random (MAR) assumption will be performed as sensitivity analyses for the primary estimand using the full analysis set and will be based on varying assumptions for missing data.

5.3.3.3.1. Tipping Point Analysis

Tipping point sensitivity analyses will be conducted to explore the potential impact of missing data and to show the robustness of the conclusion based on the primary analysis. The analysis finds a (tipping) point in the spectrum of assumptions, at which point the result changes from statistically significant to statistically non-significant.

The following method will be utilized to vary the imputation of endpoint status for missing data for the primary endpoint, after the intercurrent event strategies have been applied. For participants with missing data for the primary endpoint, the clinical remission status (responder/non-responder) will be imputed in an increasing manner by participant level for both the combined guselkumab SC induction group and the placebo group. Specifically, for each participant with missing data, a responder/non-responder status will be imputed starting with the scenario where all participants are non-responders (i.e., not in clinical remission) up to the scenario where all participants are responders (i.e., in clinical remission). This would include all possible scenarios of responder status for all missing data allowing assumptions about the missing outcomes to vary independently, including scenarios where participants randomized to guselkumab SC have worse outcomes than participants randomized to placebo SC. For each scenario, the difference in the proportion of participants achieving the primary endpoint between the combined guselkumab SC induction group and the placebo group and the corresponding p-values based on the Chi-square test will be provided.

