1.2. Study Design

This is a randomized, double-blind, placebo-controlled, parallel-group, multicenter study to evaluate the efficacy and safety of guselkumab SC induction therapy in adult participants with moderately to severely active UC defined as a modified Mayo score of 5 to 9, inclusive, Mayo rectal bleeding subscore ≥ 1 and a Mayo endoscopy subscore ≥ 2 . Participants must have demonstrated an inadequate response to or intolerance of conventional (i.e., 6-mercaptopurine (6-MP), azathioprine (AZA), or corticosteroids) or advanced therapy (ADT; i.e., tumor necrosis factor (TNF) α antagonists, vedolizumab, ozanimod, or approved Janus kinase (JAK) inhibitors). An overview over the study design is given in Figure 1.

A target of 399 participants will be enrolled in this study with 133 participants planned per intervention group. Participants who had an inadequate response to or intolerance of advanced therapy (ADT-IR) will comprise a minimum of approximately 40% and a maximum of approximately 50% of the population. Consented participants will be screened for study eligibility within 8 weeks of the Week 0 visit. Eligible participants will be randomized in a 1:1:1 ratio to the following intervention groups:

- Guselkumab CCI at Weeks 0, 4, and 8 followed by guselkumab 200 mg SC q4w through Week 24
- Guselkumab CCl at Weeks 0, 4, and 8 followed by guselkumab 100 mg SC q8w through Week 24
- Placebo SC q4w from Week 0 through Week 24

Participants will be allocated to an intervention group using permuted block randomization stratified by ADT-IR status (Yes/No) and Mayo endoscopy subscore at baseline (moderate [2] or severe [3]).

At weeks 12 and 16, all participants will be evaluated according to predefined rescue criteria as given below. All participants in the placebo group who meet rescue criteria at Week 16 will receive rescue treatment, i.e., guselkumab at Weeks 16, 20, and 24 followed by guselkumab 100 mg SC q8w. Participants randomized to guselkumab who meet rescue criteria at Week 16 will continue their assigned treatment regimen and receive blinded sham rescue with matching placebo SC injections at Weeks 16, 20, and 24.

Rescue criteria are defined as:

• No improvement (i.e., no decrease) in Mayo endoscopy subscore at Week 12, when compared with baseline

AND

• A <2 point improvement (i.e., <2 point decrease) in partial Mayo score at Weeks 12 and 16, when compared with baseline

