3. SAMPLE SIZE DETERMINATION

Sample size was determined by the power to detect significant differences in the primary endpoint of clinical remission at Week 12, and by the objective of maintaining at least 85% power across secondary endpoints at Week 12 between the combined guselkumab SC induction groups and the placebo SC group as well as for symptomatic remission at Week 24 between each guselkumab group and the placebo group, using 2-sided χ^2 tests with significance level 0.05. Combination of guselkumab SC induction groups for the primary endpoint and other Week 12 endpoints is warranted by the fact their treatment is identical through the induction period, and only differs after assessment of the primary endpoint at Week 12.

With assumed clinical remission rates of 8% for placebo and 22% for the combined guselkumab groups (based on data from Phase 2b guselkumab UC IV induction study [CNTO1959UCO3001] and Phase 3 ustekinumab UC program [CNTO1275UCO3001]), a total of 399 participants (randomized 1:1:1 for guselkumab CC q4w [Weeks 0, 4, and 8] followed by guselkumab 200 mg SC q4w: guselkumab q4w [Weeks 0, 4, and 8] followed by guselkumab 100

mg SC q8w: Placebo, yielding a 2:1 guselkumab:placebo randomization ratio for Week 12 comparisons) will ensure >95% power for the primary endpoint. This sample size also protects against a slightly lower remission rate of 20% for the combined guselkumab groups or a slightly higher remission rate of 9.5% in the placebo group (as observed in CNTO1959UCO3001), yielding a power of 90% in both cases.

Individual power values (ie, without consideration of an adjustment for multiplicity) achieved for secondary endpoints at Week 12 with a total of 399 participants (2:1 guselkumab:placebo) are described in Table 2.

Table 2: Power for Secondary Endpoints at Week 12

Endpoints	Proportion achieving endpoint in Placebo group	Proportion achieving endpoint in combined Guselkumab group	Power
Symptomatic remission	20%	45%	>99%
Endoscopic improvement	13%	28%	94%
Clinical response	30%	60%	>99%
Histologic-endoscopic mucosal improvement	8%	19%	85%
Assumed rates were based on data from the Phase 2b guselkumab UC IV induction study and the Phase 3 ustekinumab UC program			

For the secondary endpoints at Week 24, power is determined by the pairwise comparison of individual guselkumab groups to placebo (see Table 3).

Table 3: Power for Secondary Endpoints at Week 24 with a Total of 399 Participants (133 per Treatment Group)

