5.3.3. Analysis Methods

5.3.3.1. Main Estimator (Analysis) for the Primary Estimand

The analysis of the primary estimand will be based on the FAS, which includes all randomized participants who received at least 1 dose (partial or complete) of study intervention. Participants will be analyzed according to the intervention group to which they were randomized regardless of the study intervention they actually received.

Regarding the ICE strategies, for the treatment policy strategy, the associated ICE will be ignored, and any data observed after the associated ICE will be used for analysis. After accounting for the ICE strategies, participants who are missing any or all of the three subscores that comprise the primary endpoint at Week 12 will be considered not to be in clinical remission at Week 12. Participants who are missing the stool frequency subscore at baseline will be considered not to be in clinical remission at Week 12.

Summaries of the proportion of participants in clinical remission at Week 12 by treatment group along with the adjusted treatment difference between the combined guselkumab SC induction group and the placebo group, as well as the associated 95% confidence interval will be presented. Comparison against placebo will be performed in terms of the common (overall) risk difference for multiway 2x2 tables at a two-sided significance level of 0.05. Specifically, the adjusted treatment difference, 95% confidence interval, and p-value will be in terms of the common risk difference by use of Mantel-Haenszel stratum weights and the Sato variance estimator;

stratification is by ADT-IR status (Yes/No), and Mayo endoscopy subscore at baseline (moderate [2] or severe [3]).

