5.3.3.3.2. Tipping Point Based on Multiple Imputation with Bernoulli Draws

A sensitivity analysis will be performed using a tipping point analysis with Bernoulli draws to impute missing clinical remission status after the intercurrent event rules have been applied, when the number of missing participants (after accounting for the ICE strategies) is ≥ 10 in any treatment group. This tipping point analysis involves the following distinct steps:

1. Some p will be assumed for each treatment group's response rate, which could vary by treatment group, to impute the response status (Yes/No) for participants with a missing

- response based on a Bernoulli distribution. This will be repeated 500 times to generate 500 multiple imputations.
- 2. Each of the resulting data sets will be analyzed based on the common risk difference test proposed for the primary analysis.
- 3. The results from the imputed data sets will then be combined to produce inferential results based on Rubin's rules.

The analysis will be repeated for a range of values for p (for example, 0% to 30% in increments of 3% and 30% to 50% in increments of 5% independently, for both the placebo and the guselkumab groups).

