5.3.3.3. Missing at Random Multiple Imputation

Missing data for the primary estimand of the primary endpoint of clinical remission at Week 12 defined in Section 5.3.1 after the intercurrent event strategies have been applied will be summarized by intervention group. Data that is missing consists of data after discontinuation of study intervention for participants with ICEs in category 5 who do not have observed data at Week 12 and of missing data not related to ICEs.

This sensitivity analysis will evaluate the primary endpoint when all missing data as defined above are multiply imputed under the missing at random assumption. Imputation will be performed separately for all components of the primary endpoint. The following steps will be performed:

- 1. Any missing Mayo components pertaining to the primary endpoint at Week 12 will be imputed 500 times to generate 500 complete data sets using the fully conditional specification method, assuming missing at random. The following variables will be included in the imputation model: Mayo subscores at baseline and Week 12, partial Mayo subscores at Week 4 and Week 8, ADT-IR status and treatment group.
- 2. Each of the 500 resulting data sets will be analyzed using the common risk difference with Mantel-Haenszel weights, using baseline Mayo endoscopy subscore and ADT-IR status and as factors.
- 3. The results from the 500 data sets will be combined to produce inferential results based on Rubin's rules⁵⁾.

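### Both tipping-point analyses vary remission status without exempting participants whose observed Week 12 subscore already rules remission out, so their grids can contain impossible remissions in either arm

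*SAP*

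**What the plan says.** SAP 5.3.1 defines clinical remission as a joint condition: stool frequency 0 or 1 and not above baseline, rectal bleeding 0, and endoscopy 0 or 1 without friability.

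SAP 5.3.3.1 first applies the intercurrent-event strategies. It then counts as not in remission "participants who are missing any or all of the three subscores that comprise the primary endpoint at Week 12". That group includes people with one or two subscores observed.

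Three sensitivity analyses revisit the missing outcomes:

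- **5.3.3.3.1, exhaustive tipping point:** "For participants with missing data for the primary endpoint, the clinical remission status (responder/non-responder) will be imputed in an increasing manner by participant level". In each arm independently, the scenarios run from no missing participant in remission to all of them in remission.
- **5.3.3.3.2, Bernoulli tipping point:** random draws are used to "impute missing clinical remission status after the intercurrent event rules have been applied". This runs only if at least 10 participants are missing in some treatment group.
- **Missing-at-random multiple imputation:** "Imputation will be performed separately for all components of the primary endpoint".

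**The concern.** Take a participant with no Week 12 endoscopy but an observed rectal bleeding subscore of 2. No endoscopy result could put that person in remission. The component-level imputation respects this. On the natural reading of the two tipping-point sections, the same person becomes a remitter in part of the exhaustive grid and in a share of the Bernoulli draws. Three sensitivity analyses of one estimand then disagree about whose outcome is open.

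Partial missingness is plausible here. Symptom subscores come from daily diaries, while endoscopy is a separate procedure with central video review. The Week 12 windows for slotting early-discontinuation and unscheduled assessments also differ in SAP 5.1.1: days 72–99 for the partial Mayo score and 57–113 for endoscopy.

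What is at stake is how robustness is read. A grid that contains impossible cells may show a tipping scenario that could not have occurred, or may hide one that could.

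**Working it through.** **Inputs from the documents.** The plan has "A target of 399 participants will be enrolled in this study with 133 participants planned per intervention group", "yielding a 2:1 guselkumab:placebo randomization ratio for Week 12 comparisons" (266 against 133), and a two-sided 0.05 chi-square test for sizing. It states: "With assumed clinical remission rates of 8% for placebo and 22% for the combined guselkumab groups".

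**The plan's own figure.** Pooled rate = (2 × 0.22 + 0.08)/3 = 0.1733. Null SE = √[0.1733 × 0.8267 × (1/266 + 1/133)] = 0.0402. Alternative SE = √[0.22 × 0.78/266 + 0.08 × 0.92/133] = 0.0346. Power = Φ[(0.14 − 1.96 × 0.0402)/0.0346] = Φ(1.77) = 96%, against >95% stated. The same formula gives 90.1% for 20% against 8% and 89.6% for 22% against 9.5%; the plan states 90% for both.

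**Assumptions.** The documents give neither the number missing nor the split between partly and fully missing. Observed remitters are set at the planned rates: 59/266 (22%) and 11/133 (8%). Missing counts and the share ruled out are illustrative.

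**Where the exhaustive grid tips.** Uncorrected chi-square, z = difference/√[p̄(1 − p̄)(1/266 + 1/133)], with no guselkumab participant imputed to remission:

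- 7 placebo remissions added (18/133): z = 0.0865/0.0419 = 2.06, p = 0.039.
- 8 added (19/133): z = 0.0789/0.0421 = 1.87, p = 0.061.

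So 8 imputed placebo remissions are needed. The exemption does not move this boundary. It changes whether the boundary can be reached.

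**Scenarios with and without the exemption.** Number of cells = (guselkumab open + 1) × (placebo open + 1). About half of those missing are assumed ruled out by an observed subscore.

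| Missing (guselkumab/placebo) | No exemption: non-significant cells; worst p | Open after exemption | With exemption: non-significant cells; worst p |
|---|---|---|---|
| 10/5 | 0 of 66; 0.014 | 5/2 | 0 of 18; 0.002 |
| 20/10 | 12 of 231; 0.133 | 10/5 | 0 of 66; 0.014 |
| 30/15 | 78 of 496; 0.545 | 15/8 | 2 of 144; 0.061 |

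**Bernoulli version** (500 draws, Rubin's rules, unstratified because stratum data are not available; p-values carry simulation error).

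- Adverse corner: observed 48/266 and 11/133, 20/10 missing, guselkumab probability 0. At placebo probability 0.40, p = 0.077 without the exemption and 0.020 with 10/5 open. At 0.50, p = 0.110 and 0.030. At the planned rates (59/266 and 11/133) neither version tips by 0.50 (0.011 and 0.001).
- Opposite direction: observed 44/266 and 11/133, probability 0.30 in both arms, 20/10 missing, 15 of the 20 guselkumab participants ruled out and no placebo participant. Without the exemption the expected difference is (44 + 6)/266 − (11 + 3)/133 = 0.083, p = 0.030. With it, (44 + 1.5)/266 − 14/133 = 0.066, p = 0.074. Here the unrestricted analysis overstates robustness.

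**The case against.** **The SAP never says that a known failure is imputed as a remitter.** That is correct. A missing remission status could be read as one that cannot be determined, and the any-or-all wording belongs to the primary analysis. The public copy also lacks the Mayo scoring text to which 5.3.1 refers, so a relevant rule there cannot be excluded. Against this, 5.3.3.3.1 speaks of each participant with missing data and runs up to all of them responding. Even on the kinder reading, a programmer must choose a rule that changes the output.

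**A reader might infer that the impossible remissions fall mainly on placebo.** The documents do not support that. Assume 5% missing and diaries present in 70% of those, and use the complements of the planned Week 12 symptomatic remission rates (80% failing on placebo, 55% on guselkumab; SAP Table 2). Known failures are then 6.65 × 0.7 × 0.8 = 3.7 on placebo and 13.3 × 0.7 × 0.55 = 5.1 on guselkumab. Placebo is higher only as an arm rate (2.8% against 1.9%). The 80% and 55% are also too high for this use, because that endpoint already counts intercurrent events and missing data as failures.

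**A reader might also infer that the plan generally understates robustness.** It does not: the count boundary is fixed, the direction can reverse, and nothing tips at 10/5 missing.

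**The practical consequences are limited.** This stands. Every scenario of the exhaustive grid is reported, SAP 5.5.1.1 already plans a summary of missing Mayo components after intercurrent-event handling, and an inflated trigger count merely runs an extra analysis. But reported scenarios can be sorted into possible and impossible only if the counts of known failures by arm are shown beside them.

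**Conclusion.** The point holds as a gap in the rule for two sensitivity analyses. As written, neither exempts a participant whose observed subscore already excludes remission, so impossible remissions can enter in either arm. It concerns only participants left after the composite-strategy intercurrent events have been set to non-response.

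In the adverse corner, with placebo imputed up and guselkumab not, the result can look more fragile than the data allow. Impossible guselkumab remissions push the other way. Under the assumed counts, with about half ruled out, the gap changes the reading at roughly 20/10 missing or more and does not at 10/5. These sizes depend on assumed missingness, an assumed share ruled out, assumed observed rates and unstratified tests. The primary test, alpha and sample size are unaffected.

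**What to change.** In SAP 5.3.3.3.1 and 5.3.3.3.2, add one sentence: after intercurrent-event handling, a participant with at least one observed Week 12 component incompatible with remission stays a non-responder in every scenario and draw. Such components are stool frequency above 1 or above baseline, rectal bleeding above 0, endoscopy above 1, or friability.

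Vary only participants whose status is undetermined, meaning that every observed component passes or none is observed. Apply the threshold of 10 to that count. Report known-failure and undetermined counts by arm.

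The cost is one derivation flag and one sentence. The Bernoulli analysis may be triggered less often. The primary analysis and the missing-at-random analysis do not change.

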5.3.3.3.2. Tipping Point Based on Multiple Imputation with Bernoulli Draws

A sensitivity analysis will be performed using a tipping point analysis with Bernoulli draws to impute missing clinical remission status after the intercurrent event rules have been applied, when the number of missing participants (after accounting for the ICE strategies) is ≥ 10 in any treatment group. This tipping point analysis involves the following distinct steps:

1. Some p will be assumed for each treatment group's response rate, which could vary by treatment group, to impute the response status (Yes/No) for participants with a missing

- response based on a Bernoulli distribution. This will be repeated 500 times to generate 500 multiple imputations.
- 2. Each of the resulting data sets will be analyzed based on the common risk difference test proposed for the primary analysis.
- 3. The results from the imputed data sets will then be combined to produce inferential results based on Rubin's rules.

The analysis will be repeated for a range of values for p (for example, 0% to 30% in increments of 3% and 30% to 50% in increments of 5% independently, for both the placebo and the guselkumab groups).

5.3.3.3. Missing at Random Multiple Imputation

Missing data for the primary estimand of the primary endpoint of clinical remission at Week 12 defined in Section 5.3.1 after the intercurrent event strategies have been applied will be summarized by intervention group. Data that is missing consists of data after discontinuation of study intervention for participants with ICEs in category 5 who do not have observed data at Week 12 and of missing data not related to ICEs.

This sensitivity analysis will evaluate the primary endpoint when all missing data as defined above are multiply imputed under the missing at random assumption. Imputation will be performed separately for all components of the primary endpoint. The following steps will be performed:

- 1. Any missing Mayo components pertaining to the primary endpoint at Week 12 will be imputed 500 times to generate 500 complete data sets using the fully conditional specification method, assuming missing at random. The following variables will be included in the imputation model: Mayo subscores at baseline and Week 12, partial Mayo subscores at Week 4 and Week 8, ADT-IR status and treatment group.
- 2. Each of the 500 resulting data sets will be analyzed using the common risk difference with Mantel-Haenszel weights, using baseline Mayo endoscopy subscore and ADT-IR status and as factors.
- 3. The results from the 500 data sets will be combined to produce inferential results based on Rubin's rules⁵⁾.

5.3.3.4. Subgroup Analyses

To evaluate the consistency of the primary analysis, subgroup analyses based on demographics (e.g., age, sex, ethnicity, race, weight, region), baseline UC disease characteristics (e.g., UC disease duration, baseline endoscopy subscore) and baseline concomitant UC medications (e.g., baseline oral corticosteroid use, immunomodulators, and oral 5-ASA compounds), and history of UC-related medications (e.g., ADT-IR status) will be performed if sufficient participant data are available in the subgroup.

The subgroup analyses for the primary endpoint will be performed using the FAS. The following subgroup analyses will be performed:

- The consistency of intervention effect will be evaluated for the subgroups defined in Section 5.7.7, using the primary estimand and handling missing data by the rules specified in Section 5.3.3.1.
- For each of the subgroups identified in Section 5.7.7, the difference of the combined guselkumab SC groups vs. the placebo SC group relative to the primary endpoint at Week 12 will be presented using a forest plot and the associated p-values and 95% confidence intervals will be provided. The main estimator for the primary endpoint will be used. The main estimator for the primary estimand is based on the common (overall) risk difference by use of Mantel-Haenszel stratum weights, and the associated 95% confidence interval will use the Sato variance estimator. A two-sided Mantel-Haenszel test (at a significance level of 0.05) will be used to compute p-values; stratification is by ADT-IR status (Yes/No) and Mayo endoscopy subscore at baseline (moderate [2] or severe [3]) (where appropriate).

Subgroup analyses will only be performed if warranted by the number of participants in each subgroup.

Additionally, an analysis of the primary endpoint will be performed for each region, country and investigator site. This analysis will be descriptive and statistical testing will not be applied.

